## **5 Treatment**

### **5.1 Protocol requested treatment**

#### **5.1.1 Investigational treatment**

The following study treatments will be used:

#### **Investigational drug**

- Secukinumab prefilled syringes, available as a 150 mg in 1.0 mL and as a 75 mg in 0.5 mL syringes. Provided by Novartis.

#### **Reference therapies**

- Secukinumab placebo: secukinumab placebo available as 1 mL and 0.5 mL prefilled syringes, provided by Novartis in a form to match secukinumab prefilled syringes.
- Etanercept active comparator (not a biosimilar):
  - as provided centrally by a CRO or
  - as available and purchased locally

All study treatments will be labelled appropriately.

#### **5.1.2 Additional study treatment**

No additional treatment beyond investigational treatment is requested for this trial.

#### **5.2 Treatment arms**

Subjects will be randomized using a 1:1:1:1 ratio into one of the treatment arms mentioned below. Subjects randomized to secukinumab treatment arms (high dose and low dose) will receive dose according to the weight category (<25 kg, 25- <50kg,  $\geq$ 50 kg). Subjects in the two secukinumab arms weighing  $\geq$ 50kg will receive 150 mg (low dose group) and 300 mg (high dose group), 25 to <50 kg will receive 75mg (low dose group) and 150 mg (high dose group) and <25kg will receive 75mg for both dose groups. In order to maintain the treatment blind, all subjects in secukinumab or placebo arms will receive 2 s.c. injections at each dose, except for subjects <25kg weight category who will receive only 1 injection of either 75 mg secukinumab or matching placebo ([Table 5-1](#)).

**Table 5-1 Secukinumab/Placebo treatment arms and injections at each visit during Induction and maintenance epoch**

Weight category at randomization	Treatment arms	Blinded Dose (PFS)	Number of injections at each visit during Induction Epoch	Number of injections at each visit during Maintenance Epoch
<25 kg	AIN high dose	75mg/0.5mL AIN	1	1
	AIN low dose	75mg/ 0.5mL AIN	1	1
	Placebo high dose(pre assigned at randomization)	75mg/0.5mL AIN PBO	1	1*
	Placebo low dose (pre-assigned at randomization)	75mg/0.5mL AIN PBO	1	1*
25 to <50kg	AIN high dose	2x75mg/0.5mL AIN	2	2
	AIN low dose	75mg/0.5mL AIN +75mg/0.5mL AIN PBO	2	2
	Placebo high dose(pre assigned at randomization)	2x75mg/0.5mL AIN PBO	2	2*
	Placebo low dose (pre-assigned at randomization)	2x75mg/0.5mL AIN PBO	2	2*
≥50kg	AIN high dose	2x150mg/1.0ml AIN	2	2
	AIN low dose	150mg/1.0mL AIN+150mg/1.0mL AIN PBO	2	2
	Placebo high dose(pre assigned at randomization)	2x150mg/1.0mL AIN PBO	2	2*
	Placebo low dose (pre-assigned at randomization)	2x150mg/1.0 mL AIN PBO	2	2*

\*Placebo PASI 75 non responders will start receiving at Week 12 active treatment (secukinumab) high or low, as preassigned at randomization

- **Etanercept active comparator group:** S.C. etanercept 0.8 mg/kg (up to a maximum dose of 50 mg) once per week, for 51 weeks administered at home (self-injected or by caregiver) or at the study site. No subject blinding will be introduced for this arm, but the efficacy assessor will be blinded as regards to treatment assignment.
- **Secukinumab low dose group:** According to the weight category, s.c. secukinumab 75 mg (in <25 kg and 25 to <50 kg) or 150 mg (≥50 kg) injections at Randomization, Weeks 1, 2, 3, 4, 8, 12, 16, 20, 24, 28, 32, 36, 40, 44, and 48, and Placebo secukinumab at Weeks 13, 14 and 15 during the blinded phase of the study; thereafter at Week 52 and every 4 weeks during the extension treatment epoch until Week 232. Subjects and all site staff will be blinded as regards to treatment assignment and secukinumab dose levels during the induction and maintenance epochs. After data base lock for Week 52

analysis has been performed, the placebo injection will no longer be administered and the study will become open label. In the extension treatment epoch, between the site visits, subjects will be expected to perform the study treatment administrations at home. This can be self-administered by subject or by caregiver. Subjects <12 years of age must not self-administer. However, adolescents (aged 12 to  $\leq$ 18 years) can self-administer while under supervision of HCPs or caregiver/guardian. If subject/parent do not feel confident in performing treatment administration at home they are still allowed to receive study treatment administration at site.

- **Secukinumab high dose group:** According to the weight category , s.c. secukinumab 75mg (in <25 kg), 150mg (25 to <50 kg), 300 mg ( $\geq$ 50 kg) injections at Randomization, Weeks 1, 2, 3, 4, 8, 12, 16, 20, 24, 28, 32, 36, 40, 44, and 48, and Placebo secukinumab at Weeks 13, 14 and 15 during the blinded phase of the study; thereafter at Week 52 and every 4 weeks during the extension treatment epoch until Week 232. Subjects and all site staff will be blinded as regards to treatment assignment and secukinumab dose levels during the induction and maintenance epochs. After data base lock for Week 52 analysis has been performed, the placebo injection will no longer be administered and the study will become open label. In the extension treatment epoch, between the site visits, subjects will be expected to perform the study treatment administrations at home. This can be self-administered by subject or by caregiver. Subjects <12 years of age must not self-administer. However, adolescents (aged 12 to  $\leq$ 18 years) can self-administer while under supervision of HCPs or caregiver/guardian. If subject/parent do not feel confident in performing treatment administration at home they are still allowed to receive study treatment administration at site.
- **Placebo group:** Placebo secukinumab (one/two s.c. injections per dose) once per week for four weeks (at Randomization, Weeks 1, 2 and 3), followed by dosing every four weeks (Weeks 4 and 8). Subjects and the efficacy assessor will be blinded as regards to treatment assignment. At Week 12, subjects in the placebo group based on their PASI 75 response status at Week 12 will proceed as follows:
  - **PASI 75 responders on placebo** will discontinue study treatment at Week 12 and enter the treatment-free follow-up epoch for 8 weeks or until systemic therapy begins
  - **PASI 75 non-responders on placebo** will receive high dose or low dose secukinumab, according to the pre-assignment at the Randomization visit, and receive their treatment according to the weight category based on the weight measured at Week 12 visit (<25 kg, 25- <50kg,  $\geq$ 50 kg), on Weeks 12, 13, 14, 15, and then every four weeks starting at Week 16 until Week 48 during the maintenance epoch; thereafter Week 52 and every 4 weeks during the extension treatment epoch until week 232. After data base lock for Week 52 analysis has been performed, the placebo injection will no longer be administered and the study will become open label. In the extension treatment epoch, between the site visits, subjects will be expected to perform the study treatment administrations at home. This can be self-administered by subject or by caregiver. Subjects <12years of age must not self-administer. However, adolescents (aged 12 to  $\leq$ 18 years) can self-administer while under supervision of HCPs or caregiver/guardian. If

subject/parent do not feel confident in performing treatment administration at home they are still allowed to receive study treatment administration at site.

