#### Analyses by IRT dosing error

In this study, an Interactive Response Technology (IRT) error led to additional dosing of some subjects. The dosing errors happened after the primary endpoint (Week 12) assessment. Specifically, 36 patients who were assigned to the low dose and high dose secukinumab groups were dispensed active medication at Week 13, 14, 15 visits. At these visits, the patients who were randomized to active treatment groups were expected to receive placebo medication as to maintain the blind.

Analyses will be performed for the below groups of IRT error affected and not affected patients to understand the impact of overdosing caused due to the error, by using MI and pure non-responder imputation for missing data:

- AIN457 Low dose Affected
- AIN457 Low dose Not Affected
- AIN457 High dose Affected
- AIN457 High dose Not Affected

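### Table 5-1 lists active syringes for the secukinumab arms at every maintenance visit, while the arm descriptions give placebo at Weeks 13, 14 and 15: a three-dose discrepancy to reconcile

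*Protocol*

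**What the plan says.** Table 5-1 in Protocol Section 5.2 is the only table that gives syringe content by arm and weight category. Its title covers "Secukinumab/Placebo treatment arms and injections at each visit during Induction and maintenance epoch". Each row has a single entry in the blinded-dose column, followed by an injection count for induction and another under "Number of injections at each visit during Maintenance Epoch". The high-dose row at 25 to <50 kg reads "2x75mg/0.5mL AIN". The low-dose row at 50 kg and above reads "150mg/1.0mL AIN+150mg/1.0mL AIN PBO". All six secukinumab rows include active drug. The one footnote on dosing concerns the placebo rows: "Placebo PASI 75 non responders will start receiving at Week 12 active treatment (secukinumab) high or low, as preassigned at randomization".

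The arm descriptions follow in the same section. For the low-dose group they list the active weeks and then add "and Placebo secukinumab at Weeks 13, 14 and 15 during the blinded phase of the study". The high-dose description has the same provision.

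SAP Section 4.1, under the analyses by IRT dosing error, states that subjects randomized to active treatment should have had placebo at those visits to keep the blind. It reports that "36 patients who were assigned to the low dose and high dose secukinumab groups were dispensed active medication at Week 13, 14, 15 visits".

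**The concern.** One blinded-dose entry per row, applied to each visit in two epochs, cannot describe an arm whose syringe content changes for three visits. The table recognises such a change for the placebo rows, through the footnote, but not for the secukinumab rows.

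Weeks 13 to 15 are where content has to differ between arms. Under the arm descriptions, placebo non-responders who switch at Week 12 receive weekly active doses while the original secukinumab arms receive matching placebo. Section 5.2 cites this table when it explains how the injections preserve the blind, so the table would be expected to show the difference.

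At stake is a clear statement of planned exposure after Week 12, which underlies the Week 16 to 52 efficacy summaries by dose group, the safety data and the injection counts. The Week 12 endpoints are assessed before the first maintenance dose and are not involved.

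**Working it through.** **Inputs.** Dosing visits come from Protocol Section 3.1 (Maintenance Epoch) and the arm descriptions in Section 5.2. Injection totals come from Section 5.5.4. Doses by weight and arm come from Section 5.2 and Table 5-1.

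**Reproducing the protocol's own totals.** Induction visits are Randomization and Weeks 1, 2, 3, 4 and 8, which makes 6. Maintenance visits are Weeks 12, 13, 14, 15, 16, 20, 24, 28, 32, 36, 40, 44 and 48, which makes 13.

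- Induction: 6 × 1 = 6 injections (<25 kg) and 6 × 2 = 12 (25 kg and above). Section 5.5.4 states 6 and 12.
- Maintenance: 13 × 1 = 13 and 13 × 2 = 26. Section 5.5.4 states 13 and 26.

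Both match. These totals count syringes without separating active from placebo, so they fit either reading and cannot settle the question.

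**Active maintenance visits per secukinumab subject.**

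- Table 5-1 read literally: 13.
- Arm descriptions: 13 − 3 = 10.
- Difference: 3 visits, or 3/10 = 30% more under the table.
- Weeks 12 to 16 only: 5 under the table, 2 under the text (Weeks 12 and 16).
- Randomization to Week 48: 6 + 13 = 19 against 6 + 10 = 16.

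**In milligrams over the maintenance epoch.**

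| Dose per visit | Who | Text (10 × dose) | Table (13 × dose) | Difference (3 × dose) |
|---|---|---|---|---|
| 75 mg | <25 kg, both arms; 25 to <50 kg, low dose | 750 | 975 | 225 |
| 150 mg | 25 to <50 kg, high dose; ≥50 kg, low dose | 1,500 | 1,950 | 450 |
| 300 mg | ≥50 kg, high dose | 3,000 | 3,900 | 900 |

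In syringes, the difference is 3 active syringes for subjects under 25 kg and for low dose from 25 kg up (one active and one placebo per visit). It is 6 for high dose from 25 kg up (two active per visit).

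**Link to the exposure rule.** SAP Section 2.5.1 resolves injections of unknown content from the planned treatment where possible and otherwise assumes secukinumab. For the 300 mg group, where two identical syringes are due, it assumes secukinumab as planned. At Weeks 13 to 15 that plan is two active syringes under the table and two placebo syringes under the text. An unidentified record at one of these visits would therefore be counted as active, in line with the table and against the text. This touches the injection counts. Duration of exposure is computed from dates and is unaffected. The documents do not say how many such records exist.

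**The case against.** The strongest reply is that this is an omission in a summary table, not a rival dosing rule. The epoch columns are headed as injection counts, and those counts are correct at all 13 maintenance visits. The blinded-dose column carries no week label. Wherever the protocol sets out dosing week by week for the secukinumab arms, it puts placebo at Weeks 13, 14 and 15. No week-by-week text schedules active drug for them then. Sites also do not pick syringes from the table: the IRT allocates medication numbers and the packs look identical (Sections 5.3, 5.4 and 5.5.2).

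Much of this stands. It means that nobody at a site could have given extra doses simply by following Table 5-1. It does not remove the inconsistency. The column does state content, the title applies it to each visit in both epochs, and the footnote shows that content changes were meant to be marked.

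A reader might infer that the table led to the IRT error. The documents do not support this. SAP Section 4.1 attributes the event to the IRT, and the IRT specification is not among the documents. The pattern does not fit either. A literal reading of the table would reach every secukinumab subject, whereas the SAP defines unaffected groups in both dose arms. Its breakdown by weight and dose lists the 75 mg, 25 to <50 kg group only as not affected and has no group under 25 kg. The 36 patients are thus not a measure of this inconsistency. They show only that dispensing at these visits is prone to error.

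The analytic consequences of the event are already addressed. SAP Section 4.1 plans affected and not-affected comparisons, a display excluding affected subjects and an analysis setting affected results to missing. Section 2.9.1 adds adverse events by error status.

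**Conclusion.** The inconsistency is real and its size is exact: 13 against 10 active maintenance visits, or three doses per subject, worth 225, 450 or 900 mg by dose level. The count rests on two things: reading the blinded-dose column as the content for each visit, as the title says, and a subject who stays in one weight category and attends all visits.

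Its reach is limited. It concerns planned exposure, efficacy and safety after Week 12. SAP Section 4.1 places the dosing errors after the Week 12 assessment, so the co-primary and key secondary tests are not in question. Nor can a correction alter doses already given: SAP Section 2.15.5 dates the last Week 52 visit to 18 September 2019, and the current protocol, Amendment 4, is dated 18 September 2020. The value of correcting it lies in the protocol of record, the exposure derivation and any reuse of the table.

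It would go too far to conclude that children were given a second loading course because of the table, or that the table explains the IRT event.

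**What to change.** Reconcile Table 5-1 with the arm descriptions in Section 5.2, so that syringe content at Weeks 13, 14 and 15 is stated consistently for every arm and weight category, including placebo subjects who switch at Week 12. State in Section 5.2 which source governs if the two differ. Then check that the IRT dispensing specification uses the reconciled schedule. Make the same check on the SAP 2.5.1 rule for injections of unknown content, so that planned treatment at these visits has one meaning.

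No dosing rule is proposed here; that is for the sponsor to settle. The cost is one table revision and two checks, with no effect on visits, sample size or the Week 12 analyses.

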### **5.3 Treatment assignment, randomization**

At Randomization (Visit 2), all eligible patients will be randomized via Interactive Response Technology (IRT) to one of the treatment arms. The qualified site personnel will contact the IRT after confirming that the patient fulfills all the inclusion/exclusion criteria. The subject number, the weight of the subject and the age will be entered. The IRT will assign a randomization number to the patient. For the subjects who will receive secukinumab or secukinumab placebo, this number will be used to link the patient to a treatment arm and will specify a unique medication number for the package or packages of investigational treatment to be dispensed to the patient. Each subject will receive one or two packages per dispensing visit, depending on the treatment group and treatment epoch. For those subjects who will be randomized to etanercept, medication will be provided centrally (by a CRO) or purchased from the local market. The randomization number will not be communicated to the caller or other site members.

The randomization numbers will be generated using the following procedure to ensure that treatment assignment is unbiased and concealed from patients and investigator staff. A patient randomization list will be produced by the IRT provider using a validated system that automates the random assignment of patient numbers to randomization numbers. These randomization numbers are linked to the different treatment arms, which in turn are linked to medication number (for the secukinumab and the secukinumab placebo treatment arms). A separate medication list will be produced by or under the responsibility of Novartis Drug Supply Management using a validated system that automates the random assignment of medication numbers to packs containing the investigational drug(s).

#### **Stratification**

Randomization will be stratified by age and body weight collected at Randomization Visit. This stratification ensures balanced allocation of subjects to treatment groups within the age and weight strata.

The age strata is “age < 12” or “age  $\geq$  12”. The weight strata will be “body weight < 25 kg”, “25 kg  $\leq$  body weight < 50 kg” or “body weight  $\geq$  50 kg”. Stratification by age and body weight will occur at Randomization Visit. For the randomization at Randomization Visit, it will be targeted to have at least approximately 30% of the subjects in each weight stratum.

The randomization scheme for subjects will be reviewed and approved by a member of the IQS Randomization Group.

Within each weight stratum, subjects will be assigned to the high dose or the low dose treatment group for secukinumab or placebo (see [Table 5-1](#)).

### **5.4 Treatment blinding**

The secukinumab and the placebo arms are double blind (patient, investigator and assessor) until the data base lock for Week 52 analysis. However, for placebo PASI 75 responders

unblinding will occur at Week 12, since these subjects cannot continue into the Maintenance period but need to enter the post treatment follow-up period.

The etanercept arm is single (assessor) blind until the moment subjects complete the Week 52 visit and enter the follow-up period. Site staff (with the exception of the efficacy assessor), subject and sponsor are not blinded to the Etanercept arm for the entire treatment duration with Etanercept.

Any interim data analyses for the DMC or any other interim analyses which may be requested by health authorities during the blinded portion of the study will be performed without unblinding of Novartis personnel. Unblinded data will only be made available to independent Novartis/CRO individuals involved in the preparation of the interim analyses and who are not directly involved in the study conduct.

### **Secukinumab and placebo treatment arms**

Subjects, investigator staff, and data analysts will remain blinded to the identity of the treatment from the time of randomization, using the following methods: (1) Randomization data will be kept strictly confidential until the time of unblinding, and will not be accessible by anyone else involved in the study, (2) the identity of the placebo and secukinumab in prefilled syringes will be concealed by the use of study drugs that are all identical in packaging, labeling, schedule of administration, appearance, and odor.

Subjects on secukinumab arms, or those who were on placebo arm in induction and PASI 75 non-responders at Week 12, will remain blinded until Week 52 database lock.

Subjects who were on placebo arm in induction and PASI 75 responders at Week 12 will be unblinded to their treatment at Week 12, since they cannot continue into the maintenance epoch of the protocol and must enter the treatment-free follow-up. However the unblinding occurs after the primary endpoint assessments at Week 12 will have been completed.

An interim analysis will be performed before the planned IA at Week 24 and possibly before all subjects have reached the primary endpoint. In order to maintain the blind, the sponsor study team which will be directly involved in this analysis will no longer be part of the study conduct. The sponsor team members who will be involved in the study conduct after the interim data base lock, will not have access to any patient-level unblinded interim data until at least the data base lock for the next interim analysis at Week 24. The detailed procedures will be described in a separate charter.

After the interim database lock for the analysis at Week 24, designated Sponsor team members will be unblinded, whereas as mentioned earlier the subjects, investigator staff and persons performing the assessments will remain blinded until the database lock at Week 52.

### **Etanercept arm**

Person(s) performing efficacy assessments will remain blind to the identity of the treatment from the time of randomization until Week 52 visit of a patient, using the following methods: (1) Randomization data will be strictly confidential until the time of unblinding and will not be accessible by anyone else involved in the study, (2) etanercept treatment will be dispensed and administered by qualified site personnel other than the efficacy assessor (3) the efficacy assessor

will not speak to the subject or parent or other site personnel for study matters other than those associated directly with the performed efficacy assessments.

### **All treatment arms**

For all treatment groups, unblinding of site personnel during the induction and the maintenance epochs other than described above will only occur in the case of subject emergencies.

At the time of the interim evaluation of the data from the first 80 adolescent subjects by the external Data Monitoring Committee (DMC), designated Sponsor personnel (other than the study team) involved with the interim analyses will be unblinded.

After the Week 52 database lock (start of open label extension treatment), all subjects, sponsor team members, site personnel and persons performing the assessments will be unblinded for all treatment arms.

The appropriate personnel from the study site and Novartis will assess whether study treatment should be discontinued for any subject whose treatment code has been broken inadvertently for any reason. Study treatment **must** be discontinued after emergency unblinding.

